10.5 Response Criteria for Non-target Lesions

Complete Response (CR): Disappearance of all non-target lesions.

Incomplete Response/Stable Disease (IR/SD): The persistence of one or more non-target lesions.

Progressive Disease (PD): The appearance of one or more new lesions and/or unequivocal progression of existing non-target lesions.

10.6 Retrospective Response Review

MRI imaging for all patients on study will undergo retrospective central review following the completion of treatment. See [Section 14.4](#) for imaging central review requirements.

11.0 ADVERSE EVENT REPORTING REQUIREMENTS

11.1 Purpose

Adverse event (AE) data collection and reporting, which are required as part of every clinical trial, are done to ensure the safety of patients enrolled in the studies as well as those who will enroll in future studies using similar agents. Certain adverse events must be reported in an expedited manner to allow for timelier monitoring of patient safety and care. The following sections provide information about expedited reporting.

11.2 Expedited Reporting Requirements – Serious Adverse Events (SAEs)

To ensure compliance with these regulations/this guidance, as IND/IDE sponsor, NCI requires that AEs be submitted according to the timeframes in the AE reporting table assigned to the protocol, using the NCI's Adverse Event Expedited Reporting System (CTEP-AERS).

Any AE that is serious qualifies for expedited reporting. An AE is defined as any untoward medical occurrence associated with the use of a drug in humans, whether or not considered drug related. A Serious Adverse Event (SAE) is any adverse drug event (experience) occurring at any dose that results in ANY of the following outcomes:

- 1) Death.
- 2) A life-threatening adverse drug experience.
- 3) An adverse event resulting in inpatient hospitalization or prolongation of existing hospitalization (for ≥ 24 hours). This does not include hospitalizations which are part of routine medical practice.
- 4) A persistent or significant incapacity or substantial disruption of the ability to conduct normal life functions.
- 5) A congenital anomaly/birth defect.
- 6) Important Medical Events (IME) that may not result in death, be life threatening, or require hospitalization may be considered a serious adverse drug experience when, based upon medical judgment, they may jeopardize the patient or subject and may require medical or surgical intervention to prevent one of the outcomes listed in this definition.
- 7) Pregnancy (See [Section 11.9](#))

11.3 Specific Examples for Expedited Reporting

11.3.1 SAEs Occurring More than 30 Days After Last Dose of Study Drug

Any Serious Adverse Event that occurs more than 30 days after the last administration of the investigational agent/intervention **and** has an attribution of a possible, probable, or definite relationship to the study therapy must be reported according to the CTEP-AERS reporting table in this protocol.

11.3.2 Persistent or Significant Disabilities/Incapacities

Any AE that results in persistent or significant incapacity or substantial disruption of the ability to conduct normal life functions (formerly referred to as disabilities), congenital anomalies or birth defects, must be reported via CTEP-AERS if it occurs at any time following treatment with an agent under a NCI IND/IDE since these are considered serious AEs.

11.3.3 Death

Reportable Categories of Death

- Death attributable to a CTCAE term.
- Death Neonatal: A disorder characterized by cessation of life during the first 28 days of life.
- Sudden Death NOS: A sudden (defined as instant or within one hour of the onset of symptoms) or an unobserved cessation of life that cannot be attributed to a CTCAE term associated with Grade 5.
- Death NOS: A cessation of life that cannot be attributed to a CTCAE term associated with Grade 5.
- Death due to progressive disease should be reported as Grade 5 "*Disease progression*" in the system organ class (SOC) "*General disorders and administration site conditions*." Evidence that the death was a manifestation of underlying disease (e.g., radiological changes suggesting tumor growth or progression; clinical deterioration associated with a disease process) should be submitted.

Any death occurring **within 30 days** of the last dose, regardless of attribution to the investigational agent/intervention requires expedited reporting within 24 hours. Any death occurring **greater than 30 days** after the last dose of the investigational agent/intervention requires expedited reporting within 24 hours **only if** it is possibly, probably, or definitely related to the investigational agent/intervention.

11.3.4 Secondary Malignancy

A **secondary malignancy** is a cancer caused by treatment for a previous malignancy (eg, treatment with investigational agent/intervention, radiation or chemotherapy). A metastasis of the initial neoplasm is not considered a secondary malignancy.

The NCI requires all secondary malignancies that occur following treatment with an agent under an NCI IND/IDE be reported via CTEP-AERS. Three options are available to describe the event:

- Leukemia secondary to oncology chemotherapy
- Myelodysplastic syndrome
- Treatment related secondary malignancy

Any malignancy possibly related to cancer treatment (including AML/MDS) must also be reported via the routine reporting mechanisms outlined in this protocol.

11.3.4 Second Malignancy

A ***second malignancy*** is one unrelated to the treatment of a prior malignancy (and is **NOT** a metastasis from the initial malignancy). Second malignancies require **ONLY** routine reporting via CDUS unless otherwise specified.

11.3.5 Pregnancy, Pregnancy Loss, and Death Neonatal

NOTE: When submitting CTEP-AERS reports for “Pregnancy”, “Pregnancy loss”, or “Neonatal loss”, the Pregnancy Information Form, available at:

http://ctep.cancer.gov/protocolDevelopment/electronic_applications/docs/PregnancyReportForm.pdf, needs to be completed and faxed along with any additional medical information to [contact]. The potential risk of exposure of the fetus to the investigational agent(s) or chemotherapy agent(s) should be documented in the “Description of Event” section of the CTEP-AERS report.

11.3.5.1 **Pregnancy**

Patients who become pregnant on study risk intrauterine exposure of the fetus to agents that may be teratogenic. For this reason, pregnancy needs to be reported in an expedited manner via CTEP-AERS as **Grade 3 “Pregnancy, puerperium and perinatal conditions - Other (pregnancy)”** under the **“Pregnancy, puerperium and perinatal conditions”** SOC.

Pregnancy needs to be followed **until the outcome is known**. If the baby is born with a birth defect or anomaly, then a second CTEP-AERS report is required.

11.3.5.2 **Pregnancy Loss (Fetal Death)**

Pregnancy loss is defined in CTCAE as “*Death in utero*.” Any Pregnancy loss should be reported expeditiously, as **Grade 4 “Pregnancy loss” under the “Pregnancy, puerperium and perinatal conditions”** SOC. Do NOT report a pregnancy loss as a Grade 5 event since CTEP-AERS recognizes any Grade 5 event as a patient death.

11.3.5.3 **Death Neonatal**

Neonatal death, defined in CTCAE as “*Newborn death occurring during the first 28 days of birth*”, should be reported expeditiously, as **Grade 4 “Death neonatal” under the “General disorders and administration”** SOC **when the death is the result of a patient pregnancy or pregnancy in partners of men on study**. Do NOT report a neonatal death resulting from a patient pregnancy or pregnancy in

partners of men on study as a Grade 5 event since CTEP-AERS recognizes any Grade 5 event as a patient death.

11.4 Reporting Requirements for Specialized AEs

11.4.1 Baseline AEs

Although a pertinent positive finding identified on baseline assessment is not an AE, when possible it is to be documented as "Course Zero" using CTCAE terminology and grade. An expedited AE report is not required if a patient is entered on a protocol with a pre-existing condition (eg, elevated laboratory value, diarrhea). The baseline AE must be re-assessed throughout the study and reported if it fulfills expedited AE reporting guidelines.

- a. If the pre-existing condition worsens in severity, the investigator must reassess the event to determine if an expedited report is required.
- b. If the AE resolves and then recurs, the investigator must re-assess the event to determine if an expedited report is required.
- c. No modification in grading is to be made to account for abnormalities existing at baseline.

11.4.2 Persistent AEs

A persistent AE is one that extends continuously, without resolution between treatment cycles/courses.

ROUTINE reporting: The AE must be reported only once unless the grade becomes more severe in a subsequent course. If the grade becomes more severe the AE must be reported again with the new grade.

EXPEDITED reporting: The AE must be reported only once unless the grade becomes more severe in the same or a subsequent course.

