This study is a randomized comparison of response rate among patients with recurrent, refractory or progressive juvenile pilocytic astrocytomas and optic pathway gliomas who are treated with lenalidomide. Lenalidomide will be given either as a low dose (20 mg/m²/dose) or high dose (115 mg/m²/dose) regimen PO for 21 days of each 28 day cycle. Treatment will continue for a maximum of 26 cycles in the absence of disease progression or unacceptable side effects. Response will be evaluated prior to every other cycle for the first 13 cycles and prior to every third cycle for cycles 14-26. Correlation of steady state pharmacokinetic levels with patient outcome will be performed.

EXPERIMENTAL DESIGN SCHEMA

Note: Each cycle is 28 days

PD = Progressive Disease

SD = Stable Disease

PR = Partial Response

CR = Complete Response

1.0**GOALS AND OBJECTIVES (SCIENTIFIC AIMS)****1.1****Primary Objective**

To determine the objective response rate of children with recurrent, refractory or progressive juvenile pilocytic astrocytomas and optic pathway gliomas who are treated with Regimen A low-dose (20 mg/m²/dose) or Regimen B high-dose (115 mg/m²/dose) lenalidomide.

1.2**Secondary Objectives****1.2.1**

To estimate the event-free survival (EFS) (based on standard two-dimensional tumor measurements, determined by each institution) of children with recurrent, refractory or progressive juvenile pilocytic astrocytomas and optic pathway gliomas who are treated with lenalidomide.

1.2.2

To compare response categories and EFS across the 3 MR sequences (T2-weighted, FLAIR, T1-weighted post-contrast).

1.2.3

To correlate steady state pharmacokinetics of lenalidomide (1 sample obtained between Days 5-21) with objective response and EFS.

1.2.4

To evaluate toxicities of long term lenalidomide use.

2.0**BACKGROUND****2.1****Introduction/Rationale for Development**

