9.8 Analysis of Toxicity

Estimates will be obtained using life-table methods, with an event defined as the first occurrence of a primary toxicity. Time scale used in the time to first occurrence of a key acute and subacute toxicity is time in days since the start of therapy. Patients who have progression or recurrence of disease will be censored in these analyses. The rates of individual toxicities in each course of treatment, the number of patients who require a dose reduction and number of patients who come off protocol therapy due to toxicity will be summarized using standard descriptive statistical methods. To evaluate hematologic toxicity of long term lenalidomide administration adverse event data will be collected using CTCAE version 4 toxicity coding. Grade 3 or greater hematologic toxicities will be recorded per reporting period and compared between 2 lenalidomide doses

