11.4.3 Recurrent AEs

A recurrent AE is one that occurs and resolves during a cycle/course of therapy and then reoccurs in a later cycle/course.

ROUTINE reporting: An AE that resolves and then recurs during a subsequent cycle/course must be reported by the routine procedures.

EXPEDITED reporting: An AE that resolves and then recurs during a subsequent cycle/course does not require CTEP-AERS reporting unless:

- 1) The grade increases OR
- 2) Hospitalization is associated with the recurring AE.

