11.10 Routine Reporting of Adverse Events

Note: The guidelines below are for routine reporting of study specific adverse events on the COG case report forms and do not affect the requirements for CTEP-AERS reporting.

Routine reporting is accomplished via the Adverse Event (AE) Case Report Form (CRF) within the study database. For this study, routine reporting will include all CTEP-AERS reportable events and Grade 3 and higher Adverse Events.

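### The once-only routine reporting rule for persistent adverse events (Section 11.4.2) conflicts with the per-course and per-period toxicity summaries in Section 9.8

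*Combined protocol and SAP*

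**What the plan says.** Secondary objective 1.2.4 is "To evaluate toxicities of long term lenalidomide use". Treatment may run to 26 cycles.

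Section 9.8 answers the objective in several ways:
- a life-table analysis: "Estimates will be obtained using life-table methods, with an event defined as the first occurrence of a primary toxicity";
- descriptive summaries, including "The rates of individual toxicities in each course of treatment", the number of patients needing a dose reduction and the number removed for toxicity;
- for long-term hematologic toxicity: "Grade 3 or greater hematologic toxicities will be recorded per reporting period and compared between 2 lenalidomide doses".

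The data for these summaries come from routine reporting on the adverse event form. Section 11.10 sets its scope: "routine reporting will include all CTEP-AERS reportable events and Grade 3 and higher Adverse Events". It does not mention events that continue from one cycle to the next.

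Section 11.4 does. Its definition is "A persistent AE is one that extends continuously, without resolution between treatment cycles/courses", and the rule for such an event is "ROUTINE reporting: The AE must be reported only once unless the grade becomes more severe in a subsequent course". Recurrent events are treated differently in 11.4.3: "ROUTINE reporting: An AE that resolves and then recurs during a subsequent cycle/course must be reported by the routine procedures".

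**The concern.** A rate in each course needs, for every course, the number of patients who had the toxicity in that course. The rule in 11.4.2 guarantees one entry, in the course where the event began, unless the grade later rises. For a continuing Grade 3 or higher hematologic event, reporting once and recording in every reporting period cannot both be done on the same form, and nothing in the documents ranks the two instructions. Staff who complete the form would naturally work from Section 11 rather than from the analysis section.

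At stake is the part of the toxicity analysis that speaks to long-term use. Time to first occurrence, dose reductions and removals do not show whether a toxicity is still present in later cycles. Only the per-course and per-period summaries do. If they are built from entries, they can fall with cycle number while the toxicity itself continues.

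**Working it through.** The plan states no figure on this point, so there is none to reproduce. The check has two parts: which events the conflict reaches, and how large the loss could be.

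**1. Which events are exposed**

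- *Neutropenia and thrombocytopenia: largely not.* Section 4.3 lets a later cycle start only when ANC is at least 1,000/μL and platelets at least 100,000/μL. Section 5.2 uses practically the same values to call hematologic toxicity resolved. A new episode in the next cycle is therefore recurrent and is reported again under 11.4.3.
- *Lymphopenia and anemia: yes.* Section 4.3 lists no recovery criterion for either before a later cycle, and neither is named among the dose-modifying toxicities in Section 5.2. They can continue at Grade 3 across cycles. The risk list in Section 6.1 has anemia as likely (>20%) and decreased lymphocyte count as less likely (<=20%).
- *Attributed Grade 3 or 4 non-hematologic events: limited.* Section 5.1 requires a dose reduction for most of them, Section 5.0 allows two reductions, and further dose-modifying toxicity means removal. Section 9.8 counts both reductions and removals.
- *Other Grade 3 or higher non-hematologic events: yes.* Those not attributed to lenalidomide, and those on the Section 5.1 exclusion list, can continue without triggering these rules.

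**2. Size, by illustration**

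The inputs are assumptions, not document figures. Take one type of Grade 3 event that does not worsen, with onset probability *h* per cycle among patients not yet affected, lasting *D* cycles, and all patients still on therapy.

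- Onset in cycle *k*: h(1 − h)^(k−1).
- True prevalence in cycle 12: the sum of h(1 − h)^(k−1) over k = 12 − D + 1 to 12.
- Rate from new entries in cycle 12: h(1 − h)^11.

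For h = 0.02, the entry rate is 0.02 × 0.98^11 = 0.016. The last column repeats the share for h = 0.05 and h = 0.01.

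| D (cycles) | True prevalence, h = 0.02 | From entries, h = 0.02 | Share captured, h = 0.02 | Share captured, h = 0.05 to 0.01 |
|---|---|---|---|---|
| 1 | 1.6% | 1.6% | 100% | 100% |
| 2 | 3.2% | 1.6% | 49.5% | 48.7 to 49.7% |
| 3 | 4.9% | 1.6% | 32.7% | 31.6 to 33.0% |
| 6 | 10.1% | 1.6% | 15.8% | 14.6 to 16.3% |
| 12 | 21.5% | 1.6% | 7.4% | 6.2 to 7.9% |

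The share captured is close to 1/D and depends little on *h*. The proportion of patients ever affected is the same under either way of counting.

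**3. Would dates on the form solve it?**

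If the form holds onset and resolution dates, an event can be placed in every course it spans. The grade in those courses would still be missing. An event that falls from Grade 3 to Grade 1 without resolving needs no new report under 11.4.2, so carrying it forward would count it as Grade 3 throughout. Counting entries then gives too few events, and carrying forward can give too many.

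**The case against.** The strongest reply is that Section 9.8 already settles the hematologic part by having those toxicities recorded per reporting period, and that reporting an event once is not the same as counting it once. The case report forms are posted elsewhere (Section 12.0), and an onset date, a resolution date or an ongoing flag would let the statistician place one report in every course it covers. Both points have weight. The first leaves the two instructions unreconciled, because neither 11.4.2 nor 11.10 carries the exception to the people completing the form. The second leaves the later grades unknown, and Section 9.8 states no carry-forward rule.

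A reader might infer more than the documents support:

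- *That long-term toxicity as a whole will be understated.* This is not shown. It depends on how the tables are built, and the first-occurrence, dose-reduction and removal summaries need no repeat reports.
- *That neutropenia falling from Grade 3 to Grade 2 and back escapes re-reporting.* On the Section 5.2 values, a child who has met the start criteria has resolved, and the next episode is recurrent.
- *That attributed Grade 3 fatigue could run unseen through ten cycles.* Section 5 would lead to dose reductions and then removal well before that, and Section 9.8 counts both.
- *That the dose comparison is biased in a known direction.* The only between-dose toxicity comparison stated in Section 9.8 is the hematologic one. It is affected only if 11.4.2 is followed in place of per-period recording, and then for lymphopenia and anemia. The direction would depend on which arm has the longer-lasting events, which the documents do not tell us.

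**Conclusion.** The conflict between 11.4.2 and 9.8 is real and should be resolved, within a limited scope. If sites follow the once-only rule and the tables count entries, non-worsening Grade 3 or higher events that span cycles are counted only in their first course, and later-course rates for them are too low. In the illustration, entry counts capture roughly 1/D of the cycle-12 prevalence for an event lasting D cycles. If dates are collected and used, the event is placed correctly but its later grade is not known.

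This rests on three assumptions:
- lymphopenia and anemia count as hematologic toxicities in Section 9.8;
- the Section 5.2 values, written to govern the frequency of laboratory tests, also define resolution for reporting (the documents give no other definition for these counts);
- the form, which is not in the documents, does not already ask for a grade in every cycle. If it does, only the wording needs to be aligned.

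**What to change.** In Section 11.10, add a study-specific rule for routine reporting that overrides the routine part of 11.4.2: for each cycle, record the worst grade of each Grade 3 or higher adverse event present at any time in that cycle, including events continuing from an earlier cycle. In Section 9.8, state that the per-course and per-reporting-period summaries use this record, and say how a reporting period relates to a cycle. Leave the expedited rules unchanged.

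The cost is amendment wording and modest extra data entry for patients with continuing Grade 3 or higher events. No new tests are needed, since Section 7.1 already requires a CBC with differential before and weekly during each cycle.

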11.4.3 Recurrent AEs

A recurrent AE is one that occurs and resolves during a cycle/course of therapy and then reoccurs in a later cycle/course.

ROUTINE reporting: An AE that resolves and then recurs during a subsequent cycle/course must be reported by the routine procedures.

EXPEDITED reporting: An AE that resolves and then recurs during a subsequent cycle/course does not require CTEP-AERS reporting unless:

- 1) The grade increases OR
- 2) Hospitalization is associated with the recurring AE.

11.5 Exceptions to Expedited Reporting

11.5.1 Specific Protocol Exceptions to Expedited Reporting (SPEER)

SPEER: Is a subset of AEs within the Comprehensive Adverse Events and Potential Risks (CAEPR) that contains a list of events that are considered expected for CTEP-AERS reporting purposes. (Formerly referred to as the Agent Specific Adverse Event List (ASAEL).)

AEs listed on the SPEER should be reported expeditiously by investigators to the NCI via CTEP-AERS ONLY if they exceed the grade of the event listed in parentheses after the event. If the CAEPR is part of a combination IND using multiple investigational agents and has an SAE listed on different SPEERs, use the lower of the grades to determine if expedited reporting is required.

11.5.2 Special Situations as Exceptions to Expedited Reporting

An expedited report may not be required for a specific protocol where an AE is listed as expected. The exception or acceptable reporting procedures will be specified in the protocol. The protocol specific guidelines supersede the NCI Adverse Event Reporting Guidelines. These special situations are listed under the CTEP-AERS reporting table for this protocol.

11.6 **Reporting Requirements - Investigator Responsibility**

Clinical investigators in the treating institutions and ultimately the Study Chair have the primary responsibility for AE identification, documentation, grading, and assignment of attribution to the investigational agent/intervention. It is the responsibility of the treating physician to supply the medical documentation needed to support the expedited AE reports in a timely manner.

Note: All expedited AEs (reported via CTEP-AERS) must also be reported via routine reporting. Routine reporting is accomplished via the Adverse Event (AE) Case Report Form (CRF) within the study database.

11.7 **General Instructions for Expedited Reporting via CTEP-AERS**

The descriptions and grading scales found in the revised NCI Common Terminology Criteria for Adverse Events (CTCAE) version 5.0 will be utilized for AE reporting. All appropriate treatment areas should have access to a copy of the CTCAE version 5.0. A copy of the CTCAE version 5.0 can be downloaded from the CTEP website at: http://ctep.cancer.gov/protocolDevelopment/electronic_applications/ctc.htm.

An expedited AE report for all studies utilizing agents under an NCI IND/IDE must be submitted electronically to NCI via CTEP-AERS at: <https://eapps-ctep.nci.nih.gov/ctepaers>

In the rare situation where Internet connectivity is disrupted, the 24-hour notification is to be made to the NCI for agents supplied under a CTEP IND by telephone call to [contact].

In addition, once Internet connectivity is restored, a 24-hour notification that was phoned in must be entered into the electronic CTEP-AERS system by the original submitter of the report at the site.

- Expedited AE reporting timelines are defined as:
 - **24-Hour; 5 Calendar Days** - The AE must initially be reported via CTEP-AERS within 24 hours of learning of the event, followed by a complete expedited report within 5 calendar days of the initial 24-hour report.
 - **7 Calendar Days** - A complete expedited report on the AE must be submitted within 7 calendar days of the investigator learning of the event.
- Any event that results in a persistent or significant incapacity/substantial disruption of the ability to conduct normal life functions, or a congenital anomaly/birth defect, or is an IME, which based upon the medical judgment of the investigator may jeopardize the patient and require intervention to prevent a serious AE, must be reported via CTEP-AERS **if the event occurs following investigational agent administration.**

- Any death occurring within 30 days of the last dose, regardless of attribution to an agent/intervention under an NCI IND/IDE requires expedited reporting **within 24 hours**.
- Any death occurring greater than 30 days of the last dose with an attribution of possible, probable, or definite to an agent/intervention under an NCI IND/IDE requires expedited reporting **within 24 hours**.

CTEP-AERS Medical Reporting includes the following requirements as part of the report: 1) whether the patient has received at least one dose of an investigational agent on this study; 2) the characteristics of the adverse event including the *grade* (severity), the *relationship to the study therapy* (attribution), and the *prior experience* (expectedness) of the adverse event; 3) the Phase (1, 2, or 3) of the trial; and 4) whether or not hospitalization or prolongation of hospitalization was associated with the event.

Any medical documentation supporting an expedited report (eg, H & P, admission and/or notes, consultations, ECG results, etc.) MUST be faxed within 48-72 hours to the NCI. NOTE: English is strongly recommended for supporting documentation submitted to the numbers listed below in order for the NCI to meet the regulatory reporting timelines.

Fax supporting documentation **for AEs related to investigational agents supplied under a CTEP IND to: [contact]** (back-up: [contact]).

Also: Fax or email supporting documentation to COG for **all** IND studies ([contact]; email: [contact]; Attention: COG AERS Coordinator).

- **ALWAYS include the ticket number on all faxed documents.**
- **Use the NCI protocol number and the protocol-specific patient ID provided during trial registration on all reports.**

